### **5.2. Prohibited Concomitant Medications**

Subjects will not receive any antiviral therapy for HCV infection while participating in this Registry. If a subject requires HCV antiviral therapy, they will be discontinued from the Registry. There are no other concomitant medications which would preclude subjects from participating in this Registry.

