### 6.2.4. Early Termination (ET) Visit

Subjects discontinuing the Registry for any reason should undergo the Early Termination (ET) visit. Subjects will be asked to come in fasting for this visit and the following procedures will be performed and documented:

- Complete Health Related Quality of Life (HRQoL) Surveys
- Conduct limited physical exam
- Collect information for liver disease assessment
- Obtain blood samples.
- Perform transient elastography (at sites with a Fibroscan®)
- Record any serious adverse events or adverse events that are related to protocol-required procedures

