6.1.3. Primary Analysis of the Primary Endpoints

6.1.3.1. Proportion of Participants Maintaining SVR Through Week 240

Definition of Virologic Failure: Virologic failure is defined as having 2 consecutive blood samples (at least one week apart) with HCV RNA > LLOQ, or last available HCV RNA > LLOQ with no subsequent follow-up values. Date of virologic failure is the date of the first measurement if confirmed by 2 consecutive measurements, or the date of the last available HCV RNA > LLOQ with no subsequent follow-up values.

Participants who early terminated the study by a visit for a reason other than virologic failure are censored for that visit. In addition, participants who completed the study without a virologic failure are censored at the end of study by standard Kaplan-Meier (KM) methods.

Person-time pertaining to KM analysis of time to virologic failure will be calculated as: date of virologic failure (for participants who experienced virologic failure) or last day of registry (for participants who did not experience virologic failure) – registry start date + 1.

SVR end date will be the date to have HCV RNA level that was measurable during the registry study.

The KM estimate of the proportions of participants who maintained SVR, and the cumulative number of participants who experienced virologic failure, were at risk, and had been censored will be summarized by treatment group and by time point (Week 0, 24, 48, ..., 216 and 240), where Week 0 to 216 are the exact weeks elapsed since registry start date (i.e. 0, 168, 336, ..., and 1512 days), and Week 240 includes 1680 days elapsed since registry start date plus additional 30 days (i.e. 1710 days). The KM plots will also be presented in a figure.

A by-participant, by-visit listing of the actual HCV RNA value and \log_{10} HCV RNA will be provided by participant ID number in ascending order. A separate by-participant, by-visit listing of the actual HCV RNA value and \log_{10} HCV RNA will be provided for participants with virologic failure by participant ID number in ascending order, including time since registry start date to virologic failure, and time since the end of the most recent HCV treatment to virologic failure, parent study ID, most recent HCV treatment, and baseline CTP category.

Participants who experienced virologic failure more than 30 days after 240 weeks elapsed since registry start date (i.e. > 1710 days) will be listed separately.

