7.2. Others – Prior and Concomitant Medications

Participants will not receive any antiviral therapy for HCV infection while participating in this Registry. If a participant requires HCV antiviral therapy, they will be discontinued from the Registry. There are no other concomitant medications which would preclude participants from participating in this Registry. The concomitant medication records collected will be listed.

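### The SVR failure rule lets an HCV RNA value drawn after new HCV therapy cancel an unconfirmed positive, and censors exits for HCV therapy as if uninformative

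*SAP*

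**What the plan says.** SAP 6.1.3.1 gives virologic failure two limbs. The first: "Virologic failure is defined as having 2 consecutive blood samples (at least one week apart) with HCV RNA > LLOQ", dated at the first of the two. The second: "last available HCV RNA > LLOQ with no subsequent follow-up values", dated at that value. Early exits that meet neither limb fall under the censoring rule: "Participants who early terminated the study by a visit for a reason other than virologic failure are censored for that visit". Person-time for participants without failure runs to the last day of the registry, which SAP 3.8.1 takes as the last recorded visit or data date. The section also states "SVR end date will be the date to have HCV RNA level that was measurable during the registry study", but neither the event rule nor the person-time rule uses that date.

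HCV treatment is handled elsewhere. Protocol 5.2 says "If a subject requires HCV antiviral therapy, they will be discontinued from the Registry", and SAP 7.2 repeats it: "If a participant requires HCV antiviral therapy, they will be discontinued from the Registry". Neither says what such an exit means for the endpoint, and SAP 7.2 only lists the medication records.

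On exit, "Subjects discontinuing the Registry for any reason should undergo the Early Termination (ET) visit" (Protocol 6.2.4), and the procedures tables (Protocol Appendix 2, SAP Appendix 12.2) mark HCV RNA at that visit. Protocol 6.3.2 asks a subject with a value above LLOQ to return for a confirmation sample. It sets no deadline and no order relative to therapy.

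**The concern.** Everyone enters the registry in SVR (Protocol 4.1), and planned retreatment is an exclusion (Protocol 4.2). Needing HCV therapy during follow-up is therefore strong evidence of relapse or re-infection. The failure rule does not see it unless the registry samples happen to show it.

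Two histories slip through. In the first, one registry sample is above LLOQ, therapy begins before a repeat, and the early termination sample is suppressed by treatment. The positive is then neither confirmed nor the last value. In the second, viraemia is found outside the registry and treated, and no registry sample shows it. Visits are 24 weeks apart, some were missed or virtual because of COVID-19 (SAP 4.4), and the liver disease assessment in Protocol 6.3.5 does not ask for outside HCV RNA results.

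In both, the person is censored because treatment worked or began early. That is informative censoring on the first primary endpoint, durability of SVR.

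**Working it through.** The plan states no sample size, expected failure rate or durability figure, so there is nothing to reproduce. The check has two parts.

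**1. The rule applied literally.** Seven HCV RNA histories were run through SAP 6.1.3.1 with LLOQ = 15 IU/mL (SAP 3.7) and the last HCV RNA sample as the last day of registry. Each is below LLOQ up to day 168. The last column applies step 1 of the fix below by reasoning.

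| Case | Later history | SAP rule | With step 1 |
|---|---|---|---|
| A | Positive days 336 and 350, therapy, day 420 negative | Failure, day 336 | Failure, day 336 |
| B | Positive day 336, no later sample | Failure, day 336 | Failure, day 336 |
| C | Positive day 336, therapy, day 420 negative | Censored, day 420 | Failure, day 336 |
| D | Positive day 336, therapy, day 350 still positive | Failure, day 336 | Failure, day 336 |
| E | Negative day 336, positive only outside the registry, therapy, day 420 negative | Censored, day 420 | Censored no later than therapy start |
| F | As E, no sample after day 336 | Censored, day 336 | Censored no later than therapy start |
| G | Positive days 336 and 341, therapy, day 420 negative | Censored, day 420 | Failure, day 341 |

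B and C hold the same positive. The on-treatment sample alone turns a failure into a censored record, and it adds up to 420 − 336 = 84 days of follow-up without failure. In C the unused SVR end date would stop SVR at day 336 while the Kaplan-Meier analysis runs to day 420.

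No passage excludes HCV RNA drawn after new therapy starts. SAP 3.6.2, in its outlier rule, keeps all data. SAP 6.4.3 drops elastography records by their timing relative to HCV treatment, but there is no counterpart for HCV RNA.

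**2. Illustrative size.** Every input is an assumption: N = 500, 1000 or 1500; 30% other early exits; c = 2, 5 or 10 counted failures; h = 1, 3 or 5 hidden failures; all times uniform to day 1710; mean of 20 simulated data sets. The estimate is S = Π(1 − 1/rᵢ), where rᵢ is the number at risk at failure i. It was computed with the hidden cases censored and again with them as failures.

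- N = 1000, c = 5, h = 3: failure probability 0.59% becomes 0.95%; maintained SVR 99.41% becomes 99.05%.
- Hand check: the average number at risk is about 1000 × (1 − 0.30/2) = 850; 5/850 = 0.59% and 8/850 = 0.94%.
- Smallest shift: N = 1500, c = 10, h = 1, 0.80% to 0.88%, or 0.08 points.
- Largest shift: N = 500, c = 5, h = 5, 1.17% to 2.37%, or 1.20 points.
- The relative change is close to (c + h)/c: 11/10 = 1.1 at the low end and 7/2 = 3.5 at the high end, matching the simulated ratios of 1.10 and about 3.5.

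**The case against.** The documented sequence mostly works. A positive triggers a repeat sample (Protocol synopsis and 6.3.2), and once confirmed it cannot be cancelled (case A). HCV therapy is barred during participation, so the need for it should lead to exit and an early termination sample, and a viraemic sample drawn then, before treatment, counts as failure. The hidden cases need a late early termination visit, or therapy begun while still enrolled, or detection elsewhere. A missed visit can even preserve a failure, since a lone positive then stays the last value (case B). This stands: the paths are probably uncommon, and nothing in the documents would support calling them routine.

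A reader might infer that these participants are counted as SVR successes at Week 240. They are not. They are censored and leave the risk set, and their HCV RNA values, discontinuation reasons and medications are still listed.

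A reader might also infer that the whole failure rule leans one way. The documents do not establish that. The second limb counts a single unconfirmed final positive as failure, where Protocol 3.2 requires two samples, and this pulls toward less durability. The upward direction applies to the mechanism described here.

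Finally, calling therapy start a failure when no registry value is above LLOQ swaps a virologic event for a treatment decision. That is a fair objection to doing so in the main analysis, so it belongs in a sensitivity analysis.

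**Conclusion.** The gap is real and narrow. SAP 6.1.3.1 misclassifies a participant whose only positive is followed by an on-treatment value not above LLOQ, and it treats exit for HCV therapy as uninformative. Where either happens, maintained SVR is overstated. How often cannot be learned from the documents. On the assumed grid the absolute effect is about 0.1 to 1.2 percentage points, probably small, while the failure probability itself could be understated by a factor of 1.1 to 3.5. The relative effect is largest when few failures are counted. The analysis is descriptive with no hypothesis test (SAP 3.5), so no decision threshold moves. The case for correcting it is that the classification is wrong on the first primary endpoint and the remedy is cheap.

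**What to change.** 1. In SAP 6.1.3.1, state that HCV RNA collected on or after the start of any new HCV antiviral therapy is not used to confirm or cancel a failure. An unconfirmed value above LLOQ that is the last before therapy then counts as failure on its own date. Participants without failure are censored no later than therapy start.

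2. Add a sensitivity Kaplan-Meier analysis that counts discontinuation for, or start of, HCV antiviral therapy as virologic failure. Date it at the first value above LLOQ if there is one, otherwise at therapy start or discontinuation. Use the discontinuation reasons (SAP 4.1) and medication records (SAP 7.2) already planned for listing.

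Both steps are analytic and change no clinical rule. If the SAP is already final, SAP section 1 provides for documenting the change in the study report. The cost is a small amount of extra analysis and possibly a slightly less favourable durability estimate. One limit remains: therapy begun after exit may not be recorded, so some cases could stay unseen.

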3.1.2. Full Analysis Set

The Full Analysis Set (FAS) includes all participants who met all inclusion criteria and did not meet any of the exclusion criteria, and with at least one post-enrollment visit measurement available. We have 34 participants in total enrolled but not included in FAS (32 participants recorded with criteria not met in eCRF and 2 more participants who received PEG/INF in the parent study but without exclusion records in eCRF). This is the primary analysis set for endpoint analyses.

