3.6. Missing Data and Outliers

3.6.1. Missing Data

A missing data point for a given registry visit window may be due to any of the following reasons:

- A visit occurred in the window but data were not collected or were unusable
- A visit did not occur in the window
- A participant permanently discontinued from the study before reaching the window

In general, missing data will not be imputed unless methods for handling missing data are specified. Exceptions are presented in this document.

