3.8. Visit Windows

3.8.1. Definition of Visits

Baseline Value will be the first non-missing value taken on or within 30 days of the registry start date (i.e., Day 1 Visit of the registry collected from the demographic eCRF). For questionnaire data, if no data are available within 30 days after the registry start date, the baseline value will be the last non-missing value prior to the registry start date.

Study days are calculated relative to registry start date as follows:

- For measurements that are collected before the registry start date: Visit date – registry start date.
- For measurement or events that are collected on or after the registry start date: Visit date – registry start date +1.

Last Day of the registry is the last recorded non-missing visit or collected data/assessment date in the database. When determining the last day of the registry, partial date will be imputed as 01 if only day is missing and 01 January if day and month are missing.

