7. SAFETY ANALYSES

Analysis of safety measures will be descriptive and will include participants in the Safety Analysis Set. All safety data collected on or after the date of enrollment through the remainder of the study will be included.

As there was no intervention in this study, only AEs related to the required procedures by this registry were recorded. Any reference to an AE or serious adverse event (SAE) in this SAP will be referring to AEs and SAEs related to procedures required by this registry. All deaths, regardless of relatedness to study procedures were recorded when available. The immediate cause and date of death were collected when available.

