12.4.1. Data Collection

A COVID-19 supplement to the eCRF Completion Guidelines (CCG) was provided by Clinical Data Management to instruct clinical trial sites with data entry expectations pertaining to scenarios related to the COVID-19 pandemic. If a visit was missed, sites were instructed to enter “Visit missed due to COVID-19” and if an in-person visit was conducted virtually, sites were instructed to enter “Virtual visit due to COVID-19”.

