12.4.2. Determination of Missed and Virtual Visits

Natural Language Processing (NLP) will be used to search the CRF comment fields to identify instances of “COVID-19”, “Virtual”, or synonyms. The search terms will be maintained in a global lookup table and can be modified to tune the NLP model. Any comments with COVID-19 search terms, “Missed visit” or “Virtual visit will be assigned as follows:

- A) If COVID-19 terms are identified through NLP and the visit date is missing, then result is “Missed Visit”
- B) If COVID-19 and Virtual terms are identified through NLP for a visit, then result is “Virtual Visit”. When there are multiple records for the same participant and the same visit, if one record could be categorized as “Virtual Visit”, all records associated with this participant and this visit will be categorized as “Virtual Visit”
- C) Otherwise result is missing

Example Search Terms for “COVID-19” and “Virtual” Used to Identify Missed/Virtual Visits are listed below:

Search Terms for “COVID-19”	Search Terms for “Virtual”
COVID19 CORONA CORONAVIRUS PANDEMIC OUTBREAK CRISIS LOCKDOWN QUARANTINE SHELTER	VIRTUAL TELEMED TELEHEALTH TELEPHONE REMOTE TELEMEDICINE TELECONSULTATION TELEPHONICALLY PHONE HOME VISIT ZOOM SKYPE

SAP_337-1431_FINAL

ELECTRONIC SIGNATURES

Signed by	Meaning of Signature	Server Date (dd- <small>MMM</small> - <small>yyyy</small> hh:mm:ss)
PPD	Biostatistics eSigned	10-May-2022 15:05:01
PPD	Clinical Research eSigned	10-May-2022 15:56:16

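### Participants without virologic failure are censored at their last date of any data rather than their last HCV RNA result, so untested time after that result counts as at risk (minor)

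*SAP*

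**What the plan says.** SAP 6.1.3.1 defines virologic failure by HCV RNA above the LLOQ, either on two consecutive samples at least a week apart or on the last available sample. It dates the failure by a sample. For everyone else, person-time runs from registry start to the "last day of registry (for participants who did not experience virologic failure"), plus one day. SAP 3.8.1 supplies the definition: "Last Day of the registry is the last recorded non-missing visit or collected data/assessment date in the database". No HCV RNA result is required.

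The section has two other censoring sentences. Early terminators are censored for the visit by which they left, and completers at the end of study. Neither mentions HCV RNA, and nothing elsewhere cuts follow-up at the last HCV RNA.

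The estimate is tabulated by treatment group every 24 weeks. For the last row, "Week 240 includes 1680 days elapsed since registry start date plus additional 30 days (i.e. 1710 days").

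On testing, Protocol 6.3.1 and Appendix 2 schedule HCV RNA at every visit, including early termination.

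**The concern.** Kaplan-Meier censoring should fall at the last time a participant is known to be free of the event. Here that is the last HCV RNA result. At a later contact without one, virologic status is unknown, yet the participant stays in the denominator.

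The SAP leaves several routes to such a gap:

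- SAP 3.6.1 lists, among reasons for missing data, "A visit occurred in the window but data were not collected or were unusable".
- Virtual visits took place during the pandemic. SAP 12.4.1 says that "if an in-person visit was conducted virtually, sites were instructed to enter" a set comment. A virtual visit may or may not have included a blood draw.
- SAP 7 states: "All deaths, regardless of relatedness to study procedures were recorded when available". A death date can fall after the last sample.
- The Full Analysis Set needs participants only "with at least one post-enrollment visit measurement available", so someone with no post-baseline HCV RNA can enter the analysis.

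At stake are the estimate for the first-listed primary endpoint, durability of SVR, and the numbers at risk printed beside it.

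**Working it through.** **1. The plan's own figures.** The documents give no sample size, failure rate or count of untested participants, so there is no estimate to reproduce. The time points check: 240 × 7 = 1680 days, and 1680 + 30 = 1710.

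**2. Direction.** The estimator is S(t) = ∏(1 − dᵢ/nᵢ) over failure times. Keeping m untested people in the risk set changes a factor to 1 − dᵢ/(nᵢ + m), which is larger whenever dᵢ > 0. With no failure in the untested interval, no factor changes.

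Hand example: 100 participants, 20 last tested at Week 144 but with other data to Week 240, and no other losses.

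- One failure at Week 192: SVR maintained is 1 − 1/100 = 99.00% under the SAP rule and 1 − 1/80 = 98.75% with last-RNA censoring.
- One failure at Week 96 instead: all 100 are at risk under both rules, so both give 99.00%.

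**3. Size, for illustration only.** From the documents: ten post-baseline visits at 168-day steps, a ±4-week visit window, and person-time = elapsed days + 1. Assumed: constant failure rate of 0.5% per year, visit days uniform within the window, failure found at the next HCV RNA visit, and a share f with no HCV RNA at the last k visits but still contacted at Week 240. The Kaplan-Meier curve is built from expected daily events and risk sets. The assumed true failure by day 1680 is 1 − exp(−0.005 × 1680/365.25) = 2.27%.

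| Case | Day | SAP rule | Last-RNA rule | Gap (points) |
|---|---|---|---|---|
| Full testing | 1512 | 1.924% | 1.924% | 0 |
| Full testing | 1710 | 3.187% | 3.187% | 0 |
| f = 10%, k = 1 | 1512 | 1.924% | 1.927% | 0.003 |
| f = 10%, k = 1 | 1680 | 2.173% | 2.200% | 0.026 |
| f = 10%, k = 1 | 1710 | 3.074% | 3.200% | 0.126 |
| f = 5%, k = 1 | 1710 | 3.131% | 3.193% | 0.06 |
| f = 10%, k = 2 | 1512 | 1.914% | 1.937% | 0.02 |
| f = 10%, k = 2 | 1710 | 3.051% | 3.200% | 0.15 |

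Gaps are taken before rounding. Day 1680 is not a planned row; it is shown to locate where the gap arises. At day 1512 the SAP rule shows 5% more at risk for f = 10%, k = 1, and 11% more for k = 2.

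**4. Why day 1710 stands out.** A completer seen inside the window has at most 1680 + 28 + 1 = 1709 days, so none is at risk at day 1710 under either rule. Week 240 failures are divided by a shrinking risk set. This lifts the full-testing estimate to 3.19% against the assumed 2.27%, and it magnifies any difference in the denominator. For f = 10%, k = 1, about 0.10 of the 0.126 points (0.126 − 0.026) arises after day 1680. With visits on the exact day, the day-1710 gap is 0.02 points (2.251% against 2.274%).

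**The case against.** The strongest reply is that the gap may hardly occur. HCV RNA is due at every visit, and Protocol 3.2 and 6.2.4 ask anyone who discontinues to attend an early termination visit with blood samples. The wording on missing data in SAP 3.6.1 is generic. This stands: f and k are assumptions. It does not make the effect exactly zero whenever the final sample is obtained, because any later date can set the last day. One example is a return within 4 weeks for a fasting sample under Protocol 6.3.1.

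A second reply is that the rules often agree. That also stands. Simulated with f = 10%, k = 1 and an assumed treatment group of 100, the day-1710 estimates were identical in about 69% of datasets; for a group of 300 the figure was about 28%.

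A third is that the change does not bring the day-1710 figure nearer the truth. In the illustration it moves from 3.07% to 3.20%, away from 2.27%. For an assumed 1,000 participants, root mean squared error rises from about 1.9 to 2.2 points at day 1710 and stays at 0.458 at day 1512. The arithmetic is right, but the excess over 2.27% comes from completers being censored before day 1710, which happens with full testing too. Against full testing at day 1710, last-RNA censoring is 0.01 points high and the SAP rule 0.11 points low. At day 1512 with k = 2, neither rule is closer.

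Finally, no hypothesis is tested, and the HCV RNA listings and COVID-19 visit tables would help identify those affected. They would not change the estimate.

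**Conclusion.** The mismatch between the two clocks is clear from the text: failures are dated by HCV RNA samples, while non-failures are censored at a date that need not carry one. Where a gap exists, the failure estimate is equal or lower and the number at risk is inflated. The size cannot be determined from the documents and is probably small. Where the final sample is obtained it is nil or negligible; under the stated assumptions it is about 0.003 points at day 1512, 0.03 at day 1680 and 0.13 at day 1710. Severity is minor.

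Three stronger inferences are tempting and lack support:

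- **That pandemic visits created a large untested tail.** No section says virtual visits lacked samples. For missed visits, SAP 12.4.2 reads "If COVID-19 terms are identified through NLP and the visit date is missing, then result is" a missed visit; with no visit date, such a visit cannot by itself extend the last day.
- **That the plan overstates durability relative to the truth.** The comparison here is only with censoring at the last HCV RNA. In the ±4-week illustration both rules exceed the assumed true failure at day 1710.
- **That the day-1710 gap measures this issue alone.** Most of it comes from the risk set running out as completers are censored, a separate matter.

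**What to change.** In SAP 6.1.3.1, for time to virologic failure only, define person-time for participants without failure as:

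date of last non-missing HCV RNA result − registry start date + 1.

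Censor those with no post-baseline HCV RNA at baseline. Keep the last day of registry for death and for duration of follow-up. Report how many participants have a last contact later than their last HCV RNA; that count shows whether the choice mattered. The present rule can stay as an optional sensitivity analysis.

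The cost is one line of text and one derived variable, with slightly less person-time and slightly wider intervals. For an assumed 1,000 participants with f = 10%, k = 1 and ±4-week visits, the standard error goes from 0.434 to 0.435 points at day 1512 and from 1.53 to 1.68 at day 1710. The change does not address completers being censored before day 1710.
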